#### Secondary Objectives

- To compare cellular immunogenicity of the third mRNA SARS-Cov-2 vaccination will be compared to patients receiving AstraZeneca vaccination as second boost in immunosuppressed patients. T cell proliferation will be assessed, and T-cell cytokine expression will be measured using flow-cytometry following *in vitro* stimulation of peripheral blood mononuclear cells (PBMCs) with SARS-Cov-2 specific antigens.
- To assess safety of a second boost vaccination.
- To evaluate the influence of vaccination on underlying disease activity.

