## 6. STUDY DESIGN

[figure not shown]
A prospective single blind randomized controlled study will be performed. A total of 68 patients with B-cell depleting therapy (rituximab) will be enrolled in this clinical trial. Four study visits per patient will be planned.

SARS-CoV-2 VAC3 study

EudraCT 2021-002348-57

Version 4.0, 10. August 2021

After inclusion of the patients (after receiving their written informed consent) serum samples for determination of antibody levels will be obtained at least 4 weeks after the second mRNA vaccination (screening visit). All patients without detectable humoral immunity against SARS-Cov2 will be invited for a second boost vaccination within 4 weeks after the screening visit. Additional study visits are scheduled at baseline (vaccination), and at weeks 1 and 4 for assessment of humoral and cellular immunity, as well as clinical signs of adverse effects of disease activity reactivation. Patients without humoral response at week 4 will be offered participation in an extended follow-up for additional 8 weeks (i.e. at week 8 and 12 after baseline)

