## 7.2.2 Study visits

### 7.2.2.1 Screening visit (visit 1, -1-28 days, at least 4 weeks after the second immunization with mRNA SARS-CoV-2 vaccine)

The investigator will inform the subject about the procedures, risks, and benefits of the study. Participants will be informed about future visits, which will be synchronized with the appointment for the third vaccination.

Fully informed, written consent must be obtained from each subject before any assessment is performed. The subject must be allowed sufficient time to consider his/her participation in the study.

The following assessments will be performed:

- Inclusion and exclusion criteria
- Demographic data, including sex, age, weight, and height
- Medical history and concomitant medication
- Assessment of adverse reactions after the mRNA SARS-CoV-2 vaccination
- Assessment of recent COVID-19 disease
- Blood will be drawn:
  - 16 ml of blood will be drawn for PBMC isolation and determination of cellular immunity
  - 8 ml of blood will be drawn for SARS-Cov-2 antibody level detection (prior vaccination).
  - 8 ml of blood will be drawn for determination of leukocyte subpopulations
  - 8 ml of blood will be drawn for biobanking of serum
  - 20 ml of blood will be drawn for routine laboratory testing: blood count, chemistry, coagulation factors
- Pregnancy test in women with childbearing potential
  - Randomization to one of the three vaccines: mRNA SARS-CoV-2 (Biontech/Pfizer or Moderna) or vector SARS-CoV-2 vaccination (AstraZeneca)
- SARS-CoV-2 vaccine appointment

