### 7.2.2.2. Baseline visit (visit 2, week 0, max. 28 days after visit 1)

[116]

SARS-CoV-2 VAC3 study

EudraCT 2021-002348-57

Version 4.0, 10. August 2021

The following activities will be performed:

- The investigator will ask all subjects about any adverse experiences occurring since Visit 1 (screening). All adverse experiences will be documented in the CRF.
- Patients will receive a patients diary, fever thermometer and spacer
- Application of mRNA SARS-CoV-2 (Biontech/Pfizer or Moderna) or vector SARS-CoV-2 vaccine (AstraZeneca)
- Patients health status will be observed for additional 30 minutes by a clinician and a nurse in case of any acute reactions to the vaccination

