### **7.3.2 Secondary study endpoints**

The secondary endpoints of this study are:

- Overall SARS-Cov-2 antibody seroconversion rate by week 4 after vaccination boost at baseline
- Difference in overall SARS-Cov-2 antibody seroconversion rate by week 4 after vaccination boost at baseline between patient with and without B-cell repopulation.
- Antibody concentrations of SARS-CoV-2 ELISA 4 weeks after vaccination boost at baseline.
- Effect of immunosuppressive comedication on SARS-Cov-2 antibody seroconversion rate by week 4 after vaccination boost at baseline
- Evaluation of cellular immunity before and one week after the vaccination.
- Safety of vaccination boost.

SARS-CoV-2 VAC3 study

EudraCT 2021-002348-57

Version 4.0, 10. August 2021

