### 9.3 Endpoints analysis

[124]

SARS-CoV-2 VAC3 study

EudraCT 2021-002348-57

Version 4.0, 10. August 2021

The primary endpoint (difference in SARS-CoV-2 antibody seroconversion rate by week 4 after vaccination boost at baseline between third mRNA SARS-CoV-2 (Biontech/Pfizer or Moderna) and vector SARS-CoV-2 vaccine (AstraZeneca)) will be analyzed using Chi-squared Test. For the seroconversion rates, 95% confidence intervals will be calculated. All subjects with available antibody responses fulfilling the eligibility criteria will be included in the analysis.

The secondary endpoints (see section 7.3.2) will be analyzed using descriptive statistics.

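### The between-vaccine T-cell objective has no specified arm estimate, interval or baseline adjustment, and the disease-activity objective has no instrument, endpoint or analysis

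*Supplement*

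**What the plan says.** All references are to protocol V4.0, whose section 9 is the analysis plan.

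- **T-cell objective.** Under Secondary Objectives: "To compare cellular immunogenicity of the third mRNA SARS-Cov-2 vaccination will be compared to patients receiving AstraZeneca vaccination as second boost". Two kinds of readout are named there: T-cell proliferation, and cytokine expression by flow cytometry after antigen stimulation.
- **T-cell endpoint.** Section 7.3.2 lists "Evaluation of cellular immunity before and one week after the vaccination" and does not mention the arms.
- **Samples.** At screening (7.2.2.1), "16 ml of blood will be drawn for PBMC isolation and determination of cellular immunity". The same volume for the same purpose is drawn at Visit 3, one week after the dose (7.2.2.3).
- **Analysis.** Section 9.3: "The secondary endpoints (see section 7.3.2) will be analyzed using descriptive statistics". The only confidence intervals it promises are for seroconversion rates.
- **Stratification.** Section 6.5 stratifies randomisation by presence or absence of B-cell depletion. Section 9 does not use the stratum.
- **Disease-activity objective.** "To evaluate the influence of vaccination on underlying disease activity". Section 6 says the week-1 and week-4 visits also look for "clinical signs of adverse effects of disease activity reactivation". The adverse-event definitions count exacerbation of a pre-existing disease. Section 7.3.2 has no disease-activity endpoint.

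**The concern.** Each of these two objectives loses something on its way to the analysis.

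The T-cell objective is a contrast between randomised vaccines. The endpoint turns it into a before-and-after evaluation, and the analysis turns that into description. Nothing says which quantity compares the arms, how uncertain it is, or how the pre-vaccination value enters. The analyst could summarise week-1 values, changes or fold changes, and these differ in precision. With 34 patients per arm, that choice matters. Left open, it can also be made after the data are seen.

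The disease-activity objective has no measurement structured to support it. Eligibility in 6.2 is any chronic condition treated with rituximab, and the study summary names both rheumatic and neurological diseases, so no single disease-specific score is implied. Adverse-event reports can count flares. They cannot quantify change from a pre-vaccination state.

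**Working it through.** **Plan's own figure.** No precision or power figure is given for any secondary objective. The only stated figure is at least 80% power for the primary comparison, 5% against 33%, with 68 patients (9.1). With 34 per arm and two-sided alpha 0.05 (assumed, since section 9 states no alpha), the pooled-variance formula gives:

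z = (0.28·√34 − 1.96·√(2·0.19·0.81)) / √(0.05·0.95 + 0.33·0.67) = (1.633 − 1.087)/0.518 = 1.05, so power is 85.4%.

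The claim holds, and nothing below depends on it.

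**T-cell comparison: inputs.** There are 68 patients randomised 1:1 (9.1, 6.5), so n = 34 per arm. Two-sided alpha is 0.05 (assumed). The correlation r between screening and week-1 values is not in the documents, so 0.3, 0.5 and 0.7 are shown as assumptions. Results are in units of the between-patient SD of the analysed (log) value and assume complete data.

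**Formulas.**
- Variance of the adjusted arm difference relative to week-1 values alone: 1 − r². Equivalent sample-size multiplier: 1/(1 − r²).
- 95% CI half-width: 1.96·√(2/34)·√(1 − r²). Without adjustment: 1.96·0.2425 = 0.48.
- Difference detectable with 80% power: (1.96 + 0.842)·√(2/34)·√(1 − r²). Without adjustment: 0.68.
- Power for a true 0.5 SD difference: Φ(0.5/[√(2/34)·√(1 − r²)] − 1.96).
- Relative variance if simple changes from screening are compared instead: 2(1 − r).

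| r (assumed) | Variance left | Variance cut | Sample-size multiplier | CI half-width (SD) | Detectable difference (SD) | Power at 0.5 SD | Relative variance, change score |
|---|---|---|---|---|---|---|---|
| no adjustment | 1.00 | – | 1.00 | 0.48 | 0.68 | 54% | – |
| 0.3 | 0.91 | 9% | 1.10 | 0.45 | 0.65 | 58% | 1.40 |
| 0.5 | 0.75 | 25% | 1.33 | 0.41 | 0.59 | 66% | 1.00 |
| 0.7 | 0.51 | 49% | 1.96 | 0.34 | 0.485 | 82% | 0.60 |

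The last column shows why the method needs naming. The endpoint wording invites a comparison of changes. At r = 0.3 that has 40% more variance than ignoring the screening value. The covariate adjustment has less variance than the change score at each of these correlations.

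The low end of r is plausible, because vaccination may follow the screening sample by up to 28 days (7.2.2.2). Section 7.1 prints a screening window of up to 14 days, so the interval itself needs reconciling.

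**Disease activity: tracing the objective.** No arithmetic applies.
- Visit lists 7.2.2.1 to 7.2.2.5: no disease-activity score or rating at any visit. Adverse events are asked about from Visit 2 onward.
- Section 6: clinical signs of reactivation at the visits, with no instrument or definition.
- Section 7.3.2: six endpoints, none on disease activity. Safety is one of them.
- Section 9.3: covers only what 7.3.2 lists, so the objective has no analysis of its own.

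**The case against.** Several points against this are sound and limit it.

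- A reader might infer that the T-cell objective cannot be met. The documents do not support that. Summaries by arm do compare the arms, section 9.3 does not forbid intervals, and descriptive secondary analysis is acceptable in a phase II trial of 68 patients. What is missing is a specified contrast with its uncertainty.
- A reader might also infer that the pre-vaccination value is ignored altogether. It is not: the 7.3.2 endpoint includes it. It simply has no stated role in comparing the arms.
- The gain from adjustment rests on an assumed correlation and is small at the low end. This stands. The need for an arm estimate with an interval, however, does not depend on r.
- A log analysis is undefined for zero or undetectable values, and two kinds of readout are named. This stands and is handled in the fix.
- A reader might infer that disease activity is never measured. Section 6 names clinical signs of reactivation, and worsening of underlying disease is an adverse event, so data exist but are unstructured. The flow chart mentioned in 7.2.1 is not in the available text, so the absence of an instrument is established only for the written visit lists.
- Every patient is vaccinated. A between-arm model of disease activity would compare vaccines and would not estimate the influence of vaccination. This stands, so the fix uses within-patient change.

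**Conclusion.** The point holds as a mismatch between two secondary objectives and their analysis.

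For T cells, the plan specifies no between-arm estimate or interval and no use of the screening value in comparing the arms, although the sample is planned for every patient. At 34 per arm with complete data, adjustment would narrow the 95% CI half-width from 0.48 SD to 0.45, 0.41 or 0.34 SD at assumed correlations of 0.3, 0.5 or 0.7. Missing data would widen all of these.

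For disease activity, the written plan has no instrument, baseline value, endpoint or analysis beyond clinical signs and adverse-event reporting. Flares can be counted; change in disease activity cannot be quantified. This gap has no numerical size.

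Neither gap touches the primary endpoint, and neither makes the secondary analyses invalid. The change is worth making but is not critical.

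**What to change.** **Section 9.3, T cells.** For each T-cell readout named under Secondary Objectives, estimate the week-1 between-arm difference by ANCOVA, with the screening value and the B-cell randomisation stratum as covariates. Work on the log scale with a stated rule for zero or undetectable values, and report the ratio of geometric means with 95% CI. If too many values are undetectable for that, use a rank-based version. Label the results secondary, without confirmatory claim. The cost is analysis-plan wording only, since the samples are already scheduled. It should be fixed before any arm-wise T-cell data are seen.

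**Disease activity, one of two options.**
- Record a short global disease-activity rating at existing Visits 1, 3 and 4, add it to 7.3.2, and report within-patient change overall and by arm with 95% CIs. With no unvaccinated group, the overall change is a before-and-after description and should be called that. The cost is one brief rating at three existing visits, plus an amendment approved by the authority and the Ethics Committee.
- Or restrict the objective to flares reported as adverse events and tabulate them by arm. The cost is rewording one line of the objectives, handled through the same amendment process.

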#### **9.4 Missing, unused and spurious data**

Only subjects for whom data are available will be included in the statistical analysis. Missing values will neither be replaced nor estimated.

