### **6.6.1. Blinding**

All patients will be blinded. Blinding of initial treatment allocation will be maintained throughout the 4 week study period. Blinding is ensured during the routine vaccination protocol at the General Hospital Vienna, where patients will see the pre-arranged dose aliquots in syringes without reference to the type of vaccine. To facilitate the process of vaccination of full vials, patients randomized to the same vaccine will be scheduled on the same day. Blinding will be mainly performed to prevent selective drop-outs due to knowledge of treatment allocation.

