### **6.7.1 Withdrawal and replacement of subjects**

Criteria for withdrawal:

Subjects may prematurely discontinue from the study at any time. The study's premature discontinuation is to be understood when the subject did not undergo complete the last visit (study visit 4) or all pivotal assessments during the study.

Subjects must be withdrawn under the following circumstances:

SARS-CoV-2 VAC3 study

EudraCT 2021-002348-57

Version 4.0, 10. August 2021

- at their own request
- if the investigator feels it would not be in the best interest of the subject to continue
- if the subject violates conditions laid out in the consent form/information sheet or disregards instructions by the study personal

In all cases, the reason why subjects are withdrawn must be recorded in detail in the CRF and the subject's medical records. Should the study be discontinued prematurely, all study materials (complete, partially completed, and empty CRFs) will be retained.

Follow-up of patients withdrawn from the study:

In case of premature discontinuation after the start of vaccination, no further investigations concerning the study will be performed. Furthermore, participants may request that no more data will be recorded from the time point of withdrawal and that all biological samples collected in the course of the study will be destroyed.

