## 9. STATISTICAL ANALYSIS

### 9.1 Sample size considerations

According to the available number of patients at our Department, including estimates of non-responders to a standard protocol of mRNA vaccination, and expected participation rates, we will attempt to include 68 patients into this trial. Based on a Chi test comparing 3rd mRNA versus vector vaccine, this number of patients will allow to achieve at least 80% power at a minimal detectable difference of 28% (5% of responders in the mRNA vaccine group versus 33% of responders in the vector vaccine group).

For differences smaller than the minimum detectable difference statistical significance will not be possible to claim.

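### Vaccinated patients who discontinue have no week-4 sample taken and drop out of the primary analysis, which leaves it open to selective loss with no sensitivity analysis to show the effect

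*Supplement*

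**What the plan says.** All references are to protocol Version 4.0 in the Supplement, whose section 9 is the statistical analysis plan.

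- **Follow-up (6.7.1).** "In case of premature discontinuation after the start of vaccination, no further investigations concerning the study will be performed". Withdrawal may be the patient's choice. It is also mandatory when the investigator considers continuing not to be in the patient's interest, or when the patient breaches consent conditions or ignores instructions. Section 9.2 adds withdrawal for major deviations that concern safety.
- **Analysis set (9.3).** "All subjects with available antibody responses fulfilling the eligibility criteria will be included in the analysis".
- **Missing data (9.4).** "Only subjects for whom data are available will be included in the statistical analysis. Missing values will neither be replaced nor estimated".
- **Blinding (6.6.1).** Blinding is described for patients only, and its purpose is given as follows: "Blinding will be mainly performed to prevent selective drop-outs due to knowledge of treatment allocation".

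Version 4.0 defines no all-randomised analysis set, no rule for counting missing outcomes and no missing-data sensitivity analysis. Section 9.1 states no allowance for loss to follow-up.

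**The concern.** The vaccine is given once, at the baseline visit (7.2.2.2), and the week-4 antibody sample is already scheduled (7.2.2.4). For a vaccinated patient who stops early without refusing further contact, the missing outcome is created by the protocol's own rule. Some of these withdrawals are decided by the investigator, who is not stated to be blinded.

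If the losses are unrelated to arm and response, the trial only loses power. If they are related to both, the comparison of completers is biased. Section 6.6.1 shows that the authors had selective loss in mind, but blinding patients to allocation is the only protection offered. A reader of the final report would have no planned analysis showing whether the result withstands plausible losses.

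**Working it through.** **Inputs.**
- Section 9.1: "we will attempt to include 68 patients into this trial". At 1:1 (section 6.5) this is 34 per arm.
- Section 9.1: "this number of patients will allow to achieve at least 80% power", for a "minimal detectable difference of 28% (5% of responders in the mRNA vaccine group versus 33% of responders in the vector vaccine group").
- Section 9.3: the primary endpoint "will be analyzed using Chi-squared Test". The continuity correction is not specified.
- Alpha is not stated. I assume 0.05, two-sided, which fits the two-sided H1 and the 95% intervals.

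**1. The plan's own figure.** With p1 = 0.05, p2 = 0.33 and mean p = 0.19,

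power = Φ{[|p2 − p1|√n − 1.96√(2p(1 − p))] / √[p1(1 − p1) + p2(1 − p2)]}.

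At n = 34: (0.28 × 5.831 − 1.96 × 0.555)/0.518 = 1.05, so power is 85.4%. At n = 30 it is 80.5%. The stated power is reproduced, and the sample size is not in question.

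**2. Near the threshold.** Uncorrected X² = N(ad − bc)² / (product of the four margins). Tables are written mRNA vs vector.

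| Table | X² | p, uncorrected | p, Yates | p, Fisher | Difference |
|---|---|---|---|---|---|
| 3/34 vs 10/34 | 68 × 238² / (34 × 34 × 13 × 55) = 4.66 | 0.031 | 0.064 | 0.062 | 20.6 points |
| two vector responders lost: 3/34 vs 8/32 | 66 × 176² / (34 × 32 × 11 × 55) = 3.11 | 0.078 | 0.152 | 0.104 | 16.2 points |
| 2/34 vs 7/34 | 68 × 170² / (34 × 34 × 9 × 59) = 3.20 | 0.074 | 0.152 | 0.150 | 14.7 points |
| four vector non-responders lost: 2/34 vs 7/30 | 64 × 178² / (34 × 30 × 9 × 55) = 4.02 | 0.045 | 0.100 | 0.071 | 17.5 points |

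The uncorrected verdict changes in both pairs. The vector arm stays ahead throughout.

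**3. Near the planned effect.** 2/34 vs 11/34 gives X² = 68 × 306² / (34 × 34 × 13 × 55) = 7.70, p = 0.0055. Losing four vector responders (2/34 vs 7/30) leaves p = 0.045. Losing five (2/34 vs 6/29) gives X² = 3.10, p = 0.079. Ten must be lost (1/24, or 4.2%, against 5.9%) before the direction changes.

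**4. What bounds would show.** Suppose four results are missing per arm (4/34 = 12%) and 2/30 vs 10/30 are observed.
- Available cases: p = 0.010.
- Missing counted as not seroconverted (2/34 vs 10/34): p = 0.011.
- Worst case for vector (6/34 vs 10/34): p = 0.25.
- Best case for vector (2/34 vs 14/34): p = 0.0006.

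The planned analysis would report only the first of these.

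**5. Power cost of counting missing as non-response.** At 10% missing the rates become 0.9 × 5% = 4.5% and 0.9 × 33% = 29.7% with 34 per arm, and power is 80.2%. The available-case rule has 0.9 × 34 = 30.6 per arm and 81.3%. At 20% missing the figures are 74.0% and 76.4%.

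**The case against.** The case for leaving the plan alone has real substance.

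- **The risk is modest.** There is one injection, one intervening visit and a four-week endpoint, and patients do not know their allocation. The documents give no attrition rate and no comparative reactogenicity. This stands, and it limits the likely size of the problem.
- **The threshold examples are chosen.** They put every loss in one arm and one outcome class, and any 68-patient trial is fragile near p = 0.05. With Yates or Fisher, none of the four tables in step 2 is significant, so no verdict changes. For 2/34 vs 7/34 the expected responder count is 34 × 9/68 = 4.5 per arm, below the usual limit of 5 for the uncorrected test. This stands. The examples show how sensitive the result can be and do not forecast a loss.
- **Some patients cannot be followed.** Those who refuse further data recording yield no sample under any rule. This stands, and the fix exempts them.
- **Available-case analysis is pre-specified and transparent.** True, but pre-specification does not remove bias from selective loss, and part of the loss here is avoidable.

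A reader might go further in three ways that the documents do not support.

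- **That a few losses could reverse which vaccine looks better.** In the examples only the p-value crosses 0.05. Near the planned effect a change of direction takes ten selective losses.
- **That removing ineligible patients is an equal source of bias.** The criteria in 6.2 and 6.3 are mostly facts fixed before vaccination, and a patient already seropositive cannot seroconvert. There is some opening, because 7.2.2.1 places randomisation at screening, where eligibility samples are drawn, while the study summary places it at baseline. Even so, such exclusions are less likely to be selective than drop-out.
- **That the week-1 result will decide who returns.** The Research Ethics section says patients learn antibody results at once, so this is possible. Nothing in the documents shows that it affects attendance.

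**Conclusion.** The concern holds in a limited form. Sections 6.7.1, 9.3 and 9.4 together turn some obtainable outcomes into missing ones and then analyse only eligible patients with results, and nothing else in Version 4.0 offsets this. The primary comparison is exposed to selective post-vaccination loss, to a degree that the documents do not allow one to estimate.

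For a result close to the threshold, two to four selective losses can change the uncorrected chi-squared verdict. For a result near the planned effect, five are needed. These figures assume 34 per arm, two-sided alpha 0.05, no continuity correction and losses concentrated in one arm and one outcome class. The plan's power statement is sound. This is a change worth making and does not invalidate the design.

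**What to change.** - **Section 6.7.1.** Ask vaccinated participants who stop early for the scheduled week-4 antibody sample unless they withdraw consent. This leaves untouched who is withdrawn and why.
- **Sections 9.3 and 9.4, primary analysis.** Include all randomised and vaccinated participants with a week-4 result, in their allocated arm. Allow exclusion only for ineligibility established from pre-vaccination data, such as a positive screening antibody result, and decided without knowledge of arm or outcome.
- **Sections 9.3 and 9.4, sensitivity analysis.** Count missing week-4 results as not seroconverted, and report best- and worst-case bounds alongside. Keep the analysis of eligible completers as supportive.

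**Cost.** Protocol wording and a blood draw that is already scheduled. When missing counts as non-response, power at 10% missing is 80.2% against 81.3% for available cases, about one point. Keeping participants with protocol deviations may dilute the effect slightly.
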